Effect of Mindfulness Training on Mental Fatigue-Related Impairments of Endurance Performance and Inhibitory Control in Athletes: An Event-Related Potential Study

Principal Investigator: [name]

NTC: NCT05452460 Date: December 19, 2023

ABSTRACT

Purpose: This study utilized a longitudinal design to examine the effect of mindfulness training on mental fatigue-related impairments of endurance performance and inhibitory control aspect of neurocognitive functions in athletes. Methods: In this randomized controlled trial (RCT) study, specifically, fifty-three aged between 18 to 25 years of college athletes were randomly assigned to either a mindfulness training group (MT, n = 26) or a waiting-list control group (WC, n = 27) after completing the pre-test. MT group engaged mindfulness program in a 60-min session per week for eight weeks, whereas WC were asked to maintain regular life and routine training. The change in dispositional mindfulness was evaluated by Athlete Mindfulness Questionnaire (AMQ) before and after the intervention. Participants completed the two 30-min manipulation conditions by Stroop task [i.e., mental fatigue condition (MF) or control condition (CON)] in both baseline and post-intervention, respectively. Before (T1) and after (T2) the 30 min manipulations, subjective mental fatigue and mood were measured using a visual analogue scale for mental fatigue (VAS-MF) and Brunel mood scale-Chinese (BRUMS-C), respectively. The participants then completed the Flanker task [i.e., reaction time (RT) and accuracy (ACC)] and its induced ERP components (i.e., N2 and P3) were recorded, and subjective mental fatigue was evaluated by VAS-MF immediately after the Flanker task (T3). Following, endurance performance [i.e., time to exhaustion (TTE] and VO2max] of participants were evaluated using graded exercise test (GXT). Additionally, VAS for motivation in task (VAS-M) was used to evaluate motivation for completing tasks after the Flanker task and GXT. Expected results: It was hypothesized that MT will exhibit less subjective and objective of mental fatigue, and exhibit less mental fatigue-related changes in endurance performance and inhibitory control-aspect of neurocognitive functions.

METHODS

Design and Sample

This study examining mindfulness training on mental fatigue-related impairments of endurance performance and inhibitory control aspect of neurocognitive functions in athletes was registered at ClinicalTrials.gov (NCT05452460). The actual conduct of this study was from 17/2/2022 to 10/1/2023. Initially, one hundred and twenty-five potential participants were recruited via advertisements and personal contact form several sports team in Taiwan. After screening the eligibility and participation interested, the fifty-three were included in this study, and eligible participants who were (1) regular sports training at least 4 hours weekly, (2) normal or corrected-to-normal vision, (3) right-handedness, (4) no physical limitation or injury in lower limbs before and during the study, (5) no diagnosed or self-reported neurological disorders (e.g., epilepsy), (6) no diagnosed or self-reported major psychiatric illness (e.g., major depression, schizophrenia), and (6) no major previous experience with mindfulness training.

Procedure

In this study, participants visited the lab four time, they completed the two 30-min manipulation conditions by Stroop task [i.e., mental fatigue condition (MF) or control condition (CON)] in both baseline and post-intervention, respectively. Before (T1) and after (T2) the 30 min manipulations, subjective mental fatigue and mood were measured using a visual analogue scale for mental fatigue (VAS-MF) and Brunel mood scale-Chinese (BRUMS-C), respectively. The participants then completed the Flanker task [i.e., reaction time (RT) and accuracy (ACC)] and its induced ERP components (i.e., N2 and P3) were recorded, and subjective mental fatigue was evaluated by VAS-MF immediately after the Flanker task (T3). Following, endurance performance [i.e., time to exhaustion (TTE] and VO2max] of participants were evaluated using graded exercise test (GXT). Additionally, VAS for motivation in task (VAS-M) was used to evaluate motivation for completing tasks after the Flanker task and GXT.

Prior to each visit, participants received the following instructions: do not do training vigorously the day before test, do not consume a food or beverage containing caffeine and alcohol 12 h before test, and do not sleep less than 7 h before the visit.

Outcome measures

Endurance performance assessment

The graded exercise test (GXT) on treadmill (h/p/cosmos pulsar 3p, Germany) was used to assess participant's endurance performance (i.e., VO2max and exhaustion time). Bruce protocol was adopted in the test (Bruce et al., 1973). The initial speed and grade of the GXT were set at 2.74 km/hr with grade of 10% and increases speed and grade every 3 min until

participants were voluntarily exhausted. Throughout endurance task, heart rate (HR) and perception of effort were measured every 2.5 min using an HR monitor (Polar H10, Finland) and Borg's 6-20 rating of perceived exertion (RPE)(Borg, 1982) to check whether participants meet the criteria of volitional exhaustion (Beltz et al., 2016). The time to exhaustion (TTE) and Maximum oxygen consumption (VO2max) were recorded as indicator of endurance performance.

Inhibitory control aspect of cognitive functions assessments

Followed by the manipulation conditions (i.e., 30-min Stroop task), inhibitory control was evaluated by a Flanker task (Eriksen & Eriksen, 1974; Friedman & Robbins, 2021). In the Flanker task, participants were presented with five arrows and instructed to respond as quickly and accurately as possible to the direction where the middle arrow is pointing (i.e., left or right). Types of trials are the congruent (i.e., >>>>) and incongruent (i.e., <<><<>.). The reaction time (RT) and accuracy (ACC) of incongruent trial were calculated as inhibitory control behaviors performance.

Furthermore, the neuroelectric activities during the Flanker task was measured by electroencephalographic (EEG). The EEG data was recorded from a 32-electrode Quik-Cap Neo Net (Compummedics Neuroscan Inc., Charlotte, NC, USA) based upon the Neuroscan system. Additionally, the EEGLAB (V8.3)7 and ERPLAB (V8.0)8 plugins based upon MATLAB (R2022a, Mathworks Inc.) were used to perform the offline data processing. Specifically, frontally (F3/Fz/F4) mean N2 amplitude and parietally (P3/Pz/P4) mean P3 amplitude for incongruent trial were extracted as neuroelectric marker of inhibitory control.

Manipulation check

Subjective mental fatigue assessment. Both in the baseline and post-intervention, the visual analog scale for mental fatigue (VAS-MF) was used to assess changes in perceived mental fatigue before (T1) and after (T2) two separate experimental conditions (i.e., 30-min of 100% incongruent Stroop task or 100% congruent version Stroop task), and after Flanker task (T3). The VAS has been used to extensively evaluate the change in perceived mental fatigue caused by prolonged cognitive task (Brown et al., 2020; Van Cutsem et al., 2017).

Objective mental fatigue assessment. Both in the baseline and post-intervention, participants completed either a 30-min 100% incongruent Stroop task or 30-min 100% congruent Stroop task. Accuracy in both Stroop tasks was calculated as an index of objective mental fatigue (Filipas et al., 2018; Smith et al., 2015).

Dispositional mindfulness assessment

The changes in dispositional mindfulness was assessed using the 16-items (5-Likert

scale) athlete mindfulness questionnaire (AMQ)(Zhang et al., 2017). Higher mean scores indicate a higher level of dispositional mindfulness. Changes in mindfulness total scores and subscale scores from baseline to post-intervention were examined.

Mood state assessment

The change in mood state before and after manipulation conditions was assessed using the Brunel mood scale- Chinese (BRUMS-C), which contains 23 items and divided into six respective sub-scales such as anger, confusion, depression, fatigue, tension, and vigor (Zhang et al., 2014).

Statistical Analysis Plan

Specifically, all analyses followed intent-to-treat approach. The t-test (e.g., age, training experience) or chi-square test (e.g., gender, sports) were used separately to compare the difference in demographic characteristic between groups. For the manipulation check (e.g., subjective/objective mental fatigue), a four-way mixed-design ANOVA with 2 (GROUP: MT, WC) \times 2 (CONDITION: MF condition, CON condition) \times 3 (ASSESSMENT TIME: T1, T2, T3) \times 2 (Phase: baseline, post-intervention) was conducted to check the effect of manipulation on VAS-MF (i.e., subjective mental fatigue). A similar four-way mixed-design ANOVA with 2 (GROUP: MT, WC) × 2 (CONDITION: MF condition, CON condition) × 5 $(BLOCK: B1, B2, B3, B4, B5) \times 2$ (Phase: baseline, post-intervention) was conducted to check the effect of manipulation on accuracy of Stroop task (i.e., objective mental fatigue). For the primary outcomes (e.g., endurance performance, inhibitory control), the condition differences (i.e., delta value) in TTE, VO2max, and RT, ACC, N2 amplitude and P3 amplitude of Flanker task between MF condition and CON condition were calculated (CON - MF). Subsequently, the post-intervention of Δ TTE, Δ VO2, Δ RT, Δ ACC, Δ N2 and Δ P3 between groups were separately compared by one-way ANCOVA while controlling baseline of delta value. Furthermore, the one-way ANCOVA was also separately conducted to compare the post-intervention of AMQ scores and mental fatigue-related change of BRUMS-C scores between groups while controlling baseline of scores. All analyses were conducted using SPSS v.26 (SPSS Inc., Chicago, IL), with a significance level set at p < 0.05.

REFERENCE

- Beltz, N. M., Gibson, A. L., Janot, J. M., Kravitz, L., Mermier, C. M., & Dalleck, L. C. (2016). Graded exercise testing protocols for the determination of VO2max: Historical perspectives, progress, and future considerations. *Journal of Sports Medicine*, 2016, 3968393. https://doi.org/10.1155/2016/3968393
- Borg, G. A. (1982). Psychophysical bases of perceived exertion. *Medicine & Science in* Sports & Exercise, 14(5), 377–381. https://doi.org/10.1249/00005768-198205000-00012
- Brown, D. M. Y., Graham, J. D., Innes, K. I., Harris, S., Flemington, A., & Bray, S. R. (2020). Effects of prior cognitive exertion on physical performance: A systematic review and meta-analysis. *Sports Medicine*, 50(3), 497-529. https://doi.org/10.1007/s40279-019-01204-8

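### Does an injury criterion that runs on through the study conflict with the intent-to-treat statement?

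*Combined protocol and SAP*

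**What the plan says.** Under Design and Sample, the fourth eligibility condition is "no physical limitation or injury in lower limbs before and during the study". It belongs to a sentence about the outcome of screening: "the fifty-three were included in this study, and eligible participants who were", followed by the list. The other conditions are weekly training hours, vision, handedness, neurological and psychiatric history, and earlier mindfulness experience. No other condition mentions the period during the study.

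The Abstract gives the order of events. Athletes were assigned to mindfulness training (MT, 26) or "a waiting-list control group (WC, n = 27) after completing the pre-test". Then "MT group engaged mindfulness program in a 60-min session per week for eight weeks". Under Procedure, "participants visited the lab four time, they completed the two 30-min manipulation conditions by Stroop task", once in each condition at baseline and again after the intervention. Two of the four visits therefore come after assignment.

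The Statistical Analysis Plan opens by saying that "all analyses followed intent-to-treat approach". It does not define the term further. It names no per-protocol set and gives no withdrawal rule.

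**The concern.** An eligibility criterion normally closes at randomisation. This one, read literally, stays open until the last visit. If an athlete injured in week five were treated as no longer eligible and left out, someone would be dropped because of an event after assignment. The groups compared would no longer be the groups randomised, while every result still carried the intent-to-treat label.

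Such a removal would also cost more data than the injury requires. Under Procedure the treadmill test comes after the Stroop task, the fatigue and mood scales, the Flanker task and the EEG recording. An injured athlete who attended but did not run could still supply four of the six primary condition differences (reaction time, accuracy, N2 and P3). Only time to exhaustion, VO2max and the motivation rating after the treadmill test would be missing.

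**Working it through.** **1. Timing.** Randomisation follows the pre-test. The two baseline visits precede it and raise no conflict. The eight intervention weeks and the two post-intervention visits follow it, so the words do reach past assignment. That part of the concern is right.

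**2. Is the criterion a rule about the analysis?** Set the two statements side by side:

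| Place | What it governs | What it says about randomised athletes |
|---|---|---|
| Design and Sample, condition 4 | who was eligible among those screened | nothing on removal or exclusion from analysis |
| Statistical Analysis Plan, first sentence | how all analyses were done | intent-to-treat |

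Only the second statement governs the analysis. The first becomes an analysis rule only if the reader adds a step that the document does not contain. The document is dated December 19, 2023 and gives the end of conduct as 10/1/2023, so it describes a completed study. In that setting the phrase reads naturally as a description of the sample: the athletes had no lower-limb injury before or during the study. On that reading the two statements agree.

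**3. Counts.**

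- Randomised: 26 + 27 = 53.
- Included under Design and Sample: 53.
- Recruited but not included: 125 − 53 = 72, put down to eligibility and interest at screening.

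The counts leave no gap between inclusion and assignment, and no injury, removal or missed visit is reported. They do not prove that all 53 were analysed, because no analysed number is given.

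**4. How much could it matter?** This is an illustration, and every input except the arm sizes is assumed. Suppose *k* athletes in each arm are injured, their post-intervention condition difference is 1 SD lower, the correlation between baseline and post-intervention differences is 0.5, and there is no true effect.

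- *Removed from both arms alike.* The remaining athletes have the same expected value in each arm, so the shift is 0 and the false-positive rate stays at 0.050. The criterion does not distinguish between arms, so this is the modelled case closest to its wording.
- *Removed from MT only, kept in the control arm.* The control mean is lowered by *k*/27 SD and the MT mean is not. If the injured athletes' baseline difference was also 0.5 SD lower, covariate adjustment takes back 0.5 × 0.5 = 0.25 SD per athlete, which leaves 0.75 × *k*/27.

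| *k* | 0.75 × *k*/27 | *k*/27 | False-positive rate of the planned ANCOVA, simulated |
|---|---|---|---|
| 1 | 0.028 SD | 0.037 SD | 0.050 to 0.051 |
| 2 | 0.056 SD | 0.074 SD | 0.053 to 0.054 |
| 4 | 0.111 SD | 0.148 SD | 0.065 to 0.075 |

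A noncentral-t approximation that treats the arms as otherwise uniform gives somewhat higher rates, up to 0.061 for two removals and about 0.09 for four. Only several removals, all from one arm, would be noticeable, and nothing in the document suggests that.

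**The case for a change.** The best case for acting is that the label cannot be checked. The document is retrospective, and it describes the 53 by a condition that can be confirmed only when the study ends. Either none of the 53 was injured, or the 53 are those who met the condition throughout. The document never says which, gives no analysed number and states no rule for missing data. Only the sponsor knows, and the answer may be a single sentence. It can be added that the illustration does not cover training that changes the injury rate itself.

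Some of this stands. The phrase is loose, and the numbers analysed per arm ought to appear in the trial report. But the Abstract says that 53 were randomly assigned, which fits the first reading and not a sample filtered afterwards. The missing analysed number and missing-data rule are a separate gap, which would be there if the criterion ended at screening. Restoring removed athletes or relabelling outcomes as completer analyses would answer an event that nobody has reported. The unmodelled case is a fair caution, but it supplies no evidence that anyone was removed.

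**Conclusion.** The concern does not call for a change. The wording of the injury criterion extends past randomisation, but the conflict with intent-to-treat appears only if it was used to exclude randomised athletes from the analysis, and no part of the document says or implies that it was. Followed as written, the Statistical Analysis Plan keeps every athlete in the assigned group, and an analyst would read the criterion as a condition of entry or a description of the sample.

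The demonstrated effect on any result is nil. This rests on two things: the equality of the 53 included and the 53 randomised, with no loss reported, and the reading of the criterion as an eligibility statement. If the sponsor's records showed several post-assignment removals concentrated in one arm, the point would need to be reopened. Otherwise the usual participant flow in the report, giving numbers randomised and analysed per arm, settles it.

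### Intent-to-treat is claimed for every analysis, but the named ANCOVAs and repeated-measures ANOVAs become complete-case as soon as a needed value is missing, and no method is given to keep incomplete athletes

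*Combined protocol and SAP*

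**What the plan says.** The Statistical Analysis Plan opens with "Specifically, all analyses followed intent-to-treat approach". It does not define an analysis set.

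The Abstract says athletes were "randomly assigned to either a mindfulness training group (MT, n = 26) or a waiting-list control group (WC, n = 27) after completing the pre-test". Under Procedure, "participants visited the lab four time, they completed the two 30-min manipulation conditions by Stroop task" in each phase, which makes MF and CON at baseline and MF and CON after the intervention.

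For TTE, VO2max, Flanker RT and accuracy, and N2 and P3 amplitude, the Statistical Analysis Plan takes the CON minus MF difference. The post-intervention deltas "between groups were separately compared by one-way ANCOVA while controlling baseline of delta value". VAS-MF and Stroop accuracy, described as manipulation checks, are each analysed by a four-way mixed-design ANOVA. The software is SPSS v.26.

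No section mentions imputation, a likelihood-based model for incomplete data, a sensitivity analysis, or the number of athletes withdrawn or analysed.

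**The concern.** Intent-to-treat means comparing everyone randomised, in the arm assigned. An ANCOVA on a delta can use only athletes for whom both the outcome and the covariate exist. A repeated-measures ANOVA uses only athletes with every cell filled. Without imputation, both delete incomplete records. The plan therefore promises a property that its named methods have only when nothing is missing.

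Two features make missing values plausible. First, the arms differ in burden: "MT group engaged mindfulness program in a 60-min session per week for eight weeks, whereas WC were asked to maintain regular life and routine training". Second, freedom from lower-limb injury is required during the study as well as before it (Design and Sample), which could be read as allowing exclusion after randomisation.

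If loss is related to outcome and falls mainly on one arm, the comparison is no longer protected by randomisation, and a reader told that it is intent-to-treat would not know. Usable data from an athlete with only one post-intervention visit would also be thrown away.

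**Working it through.** **Inputs from the documents.** 26 MT + 27 WC = 53 randomised; four visits per athlete; randomisation after the pre-test. There is no dropout rate, SD or sample-size calculation, so the plan has no figure to reproduce beyond that sum. Every rate below is an assumption.

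**1. Data needed per athlete.**
- Primary delta ANCOVA: 2 conditions × 2 phases = 4 visit values.
- VAS-MF ANOVA: 2 conditions × 3 times × 2 phases = 12 cells.
- Stroop ANOVA: 2 conditions × 5 blocks × 2 phases = 20 cells.

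**2. Athletes left in a primary ANCOVA**, 53 × (1 − p)^k, with independent loss at rate p per visit value:

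| p | k = 2 (post-intervention visits only) | k = 4 (all visits) |
|---|---|---|
| 2% | 50.9 | 48.9 |
| 5% | 47.8 | 43.2 |
| 10% | 42.9 | 34.8 |

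The k = 2 column is the relevant one for withdrawal, because allocation followed the pre-test. The k = 4 column applies to values that can be unusable at any visit, such as an ERP recording.

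**3. Athletes left in the manipulation-check ANOVAs**, same formula, independent loss per cell:

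| p | VAS-MF, k = 12 | Stroop, k = 20 |
|---|---|---|
| 1% | 47.0 | 43.3 |
| 2% | 41.6 | 35.4 |

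These losses are upper-end figures, because cells are nested in visits. If whole visits are missed at 1%, 2% or 5%, the loss is 1 − (1 − p)^4 = 3.9%, 7.8% or 18.5%.

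**4. When does complete-case ANCOVA mislead?** Simulation with no true effect, 26 v 27, baseline–post correlation 0.3 and 0.5, 4,000 runs, loss from MT only:
- Loss at random or driven by baseline delta: bias about 0, type I error 4–6%.
- Loss ranked on post-intervention delta plus noise of equal variance (a strong dependence): losing 3, 5 or 8 MT athletes gives bias of about 0.11–0.14, 0.17–0.21 or 0.27–0.31 SD of delta, and type I error of about 7–8%, 11–13% or 19–20%.

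**5. One of two post visits missing.** Simulation of 26 v 27 with the second post visit missing depending on the first result (about 19% in MT, 5% in WC), for three sets of within-phase and between-phase correlations (0.8/0.7, 0.6/0.5, 0.8/0.75): complete-case bias 0.053, 0.067 and 0.039 SD of delta in size. A likelihood analysis of all available visits gave 0.000, 0.009 and 0.015. A separate simulation of the same situation gave about 0.08–0.10 SD against about 0, with nearly the same standard error for the two methods.

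**6. Both post visits missing.** With 20% MT withdrawal depending on the post-intervention delta (r = 0.5), ANCOVA bias was about 0.15 SD. Regression on both baseline condition values, which is what the likelihood model reduces to for such athletes, gave the same 0.15 SD.

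**7. Dilution.** If a fraction w of MT withdraws and gains nothing, a completers-only effect exceeds the all-randomised effect by 1/(1 − w): 1.11, 1.18 and 1.25 for w = 10%, 15% and 20%.

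**The case against.** The strongest reply is that the text contains no contradiction. Intent-to-treat concerns who is analysed and in which arm; imputing first and then running ANCOVA or ANOVA would be compatible with it, and an unreported imputation cannot be ruled out. That stands as a limit on what can be said about the results. It does not rescue the plan, because a plan that relies on imputation has to name it.

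Several other points stand:
- No withdrawal, missed visit or exclusion is documented. A reader might infer that athletes were in fact dropped. The documents do not show that, and with nothing missing complete-case and intent-to-treat coincide.
- A reader might infer from the eight weekly sessions that MT lost its least engaged athletes and that the result is tilted towards MT. Burden makes this possible, not established. WC could lose athletes too, and a tilt also requires loss related to outcome beyond what arm and baseline delta explain.
- A reader might carry the large losses in step 3 over to the primary outcomes. A missed rating or block affects only its own manipulation-check ANOVA.
- A baseline value missing at the pre-test arose before allocation, so it is not selective loss by arm.
- A mixed model does not repair outcome-related loss of both post visits (step 6). Where only one is missing, the gain is modest: with an assumed standard error of 0.28–0.30, a bias of 0.04–0.07 SD moves type I error from 5% only to about 5.2–5.8%.
- An unstructured covariance is impractical for the ANOVA outcomes: 12 × 13/2 = 78 and 20 × 21/2 = 210 parameters from 53 athletes.

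**Conclusion.** The concern holds in a limited form. The plan claims intent-to-treat, yet the only methods it names delete incomplete records and nothing in the documents keeps those records in. If any needed value is missing, the results are complete-case, possibly in a different set for each outcome.

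Whether this changed anything cannot be determined from the documents. Under the assumed rates, a primary ANCOVA would keep about 43 to 51 of 53 athletes when 2–10% of post-intervention visits are missed. Bias would run from about zero (loss explained by arm and baseline delta) through 0.04–0.10 SD of delta (one post visit missing depending on the other) to 0.11–0.21 SD (three to five MT athletes lost in strong relation to outcome). Selective loss from MT is a risk to be checked, not a finding. The point should be corrected, with medium confidence that it matters in practice; if no data are missing, one sentence saying so settles it.

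**What to change.** 1. **Primary outcomes.** Fit a linear mixed model by REML (SPSS MIXED) to all available condition-level values (MF and CON, baseline and post) of the 53 randomised athletes in their assigned arms, with a common baseline mean and an unstructured 4 × 4 covariance (4 × 5/2 = 10 parameters). Test the same contrast: the group difference in post-intervention CON minus MF. Include post-intervention data from athletes who stopped attending MT.
2. **VAS-MF and Stroop accuracy.** Replace the listwise ANOVAs with a mixed model that has a parsimonious covariance, for example random athlete and visit effects.
3. **Sensitivity analysis.** Because the mixed model cannot correct outcome-related loss of both post visits, add one analysis in which MT athletes without post-intervention data take the WC distribution.
4. **Reporting.** Give randomised and analysed numbers by arm for each outcome, and state how missing values were handled.
5. **If the listwise models are kept and data are missing,** replace the intent-to-treat label with complete-case, as randomised.

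The cost is SAP wording and re-running models in the software already named, with no new data, visits or participants. The model is slightly more complex and the estimated MT effect may be somewhat smaller. Study conduct ended on 10/1/2023, so the counts should already be obtainable; if results are already known, the new models must be labelled post hoc. If nothing is missing, the conclusions will be essentially unchanged.

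### The mindfulness effect on mental fatigue is tested only through change-score terms in two four-way ANOVAs, although the SAP uses the more precise baseline-adjusted ANCOVA for every other outcome with a named analysis

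*Combined protocol and SAP*

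**What the plan says.** The expected-results part of the Abstract makes two predictions. The first concerns fatigue itself: "It was hypothesized that MT will exhibit less subjective and objective of mental fatigue". The second concerns performance: the trained group should "exhibit less mental fatigue-related changes in endurance performance and inhibitory control-aspect of neurocognitive functions".

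The Statistical Analysis Plan section handles the two fatigue measures as manipulation checks. VAS-MF goes into a GROUP x CONDITION x TIME x PHASE ANOVA with three time levels ("ASSESSMENT TIME: T1, T2, T3"), which "was conducted to check the effect of manipulation on VAS-MF (i.e., subjective mental fatigue". Stroop accuracy goes into a similar model with five blocks in place of time, which "was conducted to check the effect of manipulation on accuracy of Stroop task (i.e., objective mental fatigue". In both models baseline is one of the two levels of PHASE. No term is singled out as the test of mindfulness.

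The other outcomes with a named analysis are treated differently. The post-intervention CON-minus-MF deltas for TTE, VO2max, RT, ACC, N2 and P3 "between groups were separately compared by one-way ANCOVA while controlling baseline of delta value". For the questionnaires, "the one-way ANCOVA was also separately conducted to compare the post-intervention of AMQ scores" and the fatigue-related change in BRUMS-C, again controlling for baseline. VAS-M is collected, but the SAP names no analysis for it.

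**The concern.** Whether the Stroop task induced fatigue and whether mindfulness training reduced it are separate questions. The ANOVAs suit the first. For the second, the relevant information lies in the terms containing both GROUP and PHASE, and with a two-level PHASE factor these compare change from baseline. In a randomised trial, ANCOVA on the same contrast answers the same question with a smaller variance unless the baseline-to-post correlation is very high. The plan already uses that method elsewhere, and the baseline values are in hand. What is at stake is some avoidable loss of power on a stated, non-primary hypothesis with 26 and 27 participants per group.

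**Working it through.** **Inputs.** From the Abstract: n = 26 (MT) and 27 (WC). From the SAP: significance level 0.05, taken as two-sided because the F-tests are non-directional. The documents give no power calculation, effect size, SD or correlation, so there is no figure of the plan's own to reproduce. Three things are assumed: the standardised effect d (in SDs of the contrast), the baseline-to-post correlation rho of the contrast, and equal variance at baseline and post-intervention.

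**Step 1: what the terms test.** Each ANOVA has four terms containing both GROUP and PHASE. Two have one degree of freedom. GROUP x PHASE is a t-test on change in the participant's overall mean; on simulated 2x2x3x2 data with these group sizes, F and the squared t both came to 0.01521. GROUP x PHASE x CONDITION is a t-test on change in the difference between conditions.

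**Step 2: relative precision on one contrast.** With contrast variance s²:
- change score: 2(1-rho)s²
- ANCOVA: (1-rho²)s²
- ratio, ANCOVA to change score: (1-rho²)/[2(1-rho)] = (1+rho)/2

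The ratio is 0.50 at rho 0, 0.60 at 0.2, 0.75 at 0.5 and 0.95 at 0.9.

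**Step 3: what rho is likely for each term.** Suppose a fraction p of single-cell variance is a stable person effect and the rest is independent error. The mean of k cells then has rho = p/[p + (1-p)/k]. GROUP x PHASE averages 2 x 3 = 6 cells per phase for VAS-MF and 2 x 5 = 10 for Stroop accuracy.
- p = 0.5, k = 10: 0.5/0.55 = 0.91
- p = 0.3, k = 10: 0.3/0.37 = 0.81
- p = 0.2, k = 6: 0.2/0.333 = 0.60

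In the difference between conditions the person effect cancels, so under this structure rho is 0. If participants differ consistently in how they respond to the condition, rho rises above 0.

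**Step 4: power.** The noncentrality is d²/[v(1/26 + 1/27)], with 1/26 + 1/27 = 0.0755. For the change score, v = 2(1-rho) with 51 error df. For ANCOVA, v = (1-rho²)(1 + 1/49) with 50 error df; the last factor is the small-sample cost of estimating the covariate slope. Example at d = 0.8 and rho = 0: 0.64/(2 x 0.0755) = 4.24 for change and 0.64/(1.0204 x 0.0755) = 8.31 for ANCOVA.

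| Contrast | d | rho | ANCOVA | Change score |
|---|---|---|---|---|
| Mean over conditions | 0.5 | 0.91 | 98.9% | 98.7% |
| Mean over conditions | 0.5 | 0.81 | 85.5% | 82.7% |
| Mean over conditions | 0.5 | 0.60 | 59.8% | 51.4% |
| Condition difference | 0.8 | 0 | 81% | 52% |
| Condition difference | 0.8 | 0.2 | 82% | 62% |
| Condition difference | 0.8 | 0.5 | 90% | 82% |

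Simulation of 20,000 trials per setting (rho 0.3, 0.5 and 0.7) gave type I error of 4.7% to 5.2% for both methods. With the small-sample factor included, the ANCOVA advantage vanishes at rho of about 0.95 to 0.98.

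**The case against.** The strongest reply is that both analyses are valid and unbiased, that the ANOVAs are labelled manipulation checks, and that choosing between change score and ANCOVA is close to preference. Much of this stands. It limits the point to precision on secondary measures, and it rules out a large loss for GROUP x PHASE if participants have stable levels of fatigue or accuracy. It does not remove the point. The Abstract states a hypothesis about fatigue, these ANOVAs are the only analyses named for it, and the plan itself prefers ANCOVA elsewhere.

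A second reply is that BRUMS-C has a fatigue subscale and is already analysed by ANCOVA. That is true, but the protocol classes it as mood, and the SAP identifies subjective mental fatigue with VAS-MF.

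A third is that any single contrast is blind to some effects, and that its choice can matter more than the adjustment. This also stands. A CON-MF difference has only about 5% power, the false-positive rate, if mindfulness shifts both conditions equally. The fatigue half of the hypothesis is not expressly confined to that difference.

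A reader might also infer that, because no term is named, any significant GROUP-by-PHASE term could be claimed as success and the false-positive rate is inflated. The SAP states no such rule. The missing name is a gap in detail, and no error rate should be attached to it. Nor do the documents support reading the ANOVAs as biased or the fatigue hypothesis as untested.

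**Conclusion.** The point holds as a minor one. The two fatigue measures are the only outcomes with a named analysis for which baseline is a factor level and not a covariate, and this costs precision on any given contrast. The size depends on rho, which is not given. The cost is probably small for the mean over conditions, and may be material for the condition difference: between 29 and 8 percentage points of power at 0.8 SD as rho goes from 0 to 0.5. These figures rest on the assumed effect sizes, on equal baseline and post-intervention variances and, for the likely rho of each term, on the stable-person-effect model. The planned ANOVAs remain valid, and the primary comparisons do not depend on them.

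**What to change.** Keep both ANOVAs as manipulation checks. For each measure, test the mindfulness effect by one-way ANCOVA of the post-intervention CON-MF difference, with the same difference at baseline as covariate. This is the delta form that the SAP already uses. For VAS-MF, take the mean of T2 and T3, the two ratings after the manipulation (the protocol places the last one as "and after Flanker task (T3"). For Stroop accuracy, take the mean over B1 to B5. The VAS-MF contrast leaves out T1, so it is close to, but not identical with, the GROUP x PHASE x CONDITION term.

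Report alongside, with a confidence interval, the matching ANCOVA on the mean over both conditions, because the difference cannot show an effect common to both.

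The Design and Sample section has conduct ending on 10/1/2023, and the document is dated December 19, 2023. The tests should therefore be labelled post hoc unless an earlier dated plan names them.

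The cost is a few lines of SAP text and two to four extra ANCOVAs on data already collected, each using one degree of freedom for the covariate. The extra tests add some multiplicity, which is why one contrast per measure should be named as the test and the other given as an estimate.
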